#### **3.2.2. Secondary Outcome Measures**

- Change in best ear hearing assessments [improved + no change (normal to normal) versus other; improved versus other; worse + no change (abnormal to abnormal) versus other; and worse versus other] between Baseline and Study Month 6
- Change in total ear hearing assessments (improved versus other; worse + no change (abnormal to abnormal) versus other; and worse versus other) between Baseline and Study Month 6
- Detection of viruria by PCR six weeks and six months after trial entry

- The quantitative log reduction in viruria detected after 6 weeks of therapy
- Detection of viremia by PCR six weeks and six months after trial entry
- The quantitative log reduction in viremia detected after 6 weeks of therapy
- Detection of CMV in saliva by PCR six weeks and six months after trial entry
- The quantitative log reduction in CMV viral load in saliva detected after 6 weeks of therapy
- Correlation of change in viral load with change in total ear and best ear hearing at 6 months
- Incidence of unanticipated medically attended visits occurring from Study Day 1 through two weeks following the last dose of study drug
- Incidence of adverse events which lead to permanent discontinuation of valganciclovir therapy or have an unresolved outcome

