#### **8.2.1.1. Hematology Safety Labs**

All hematology safety laboratory assessments will be conducted at the PI's local lab. These assessments will provide information on the safety of administering the study drug. They will be collected at each study visit while the study subject is receiving valganciclovir and at the two week visit thereafter. The following will be tested: white blood cell count, differential, hemoglobin, and platelet count. The total amount of blood required for the hematology safety labs is 2.5 mL over 8 weeks.

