#### **9.2.2. Documentation of Reportable Adverse Events**

Information to be collected on reportable AEs includes event description, time of onset, clinician's assessment of severity, relationship to study product (assessed only by those with the training and authority to make a diagnosis, which would include MD or DO), and time of

resolution/stabilization of the event. All AEs occurring from Study Day 1 through four weeks following the last dose of study drug must be documented appropriately regardless of relationship. All AEs will be followed to adequate resolution. SAE reporting is described in section 9.5.

Any medical condition that is present at the time that the patient is randomized should be considered as a baseline condition and not reported as an AE. However, if the event meets the criteria in Section 9.2.1 and the grade of the event worsens at any time during the study, it should be recorded as an AE.

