### **9.5.2. Reporting Interval**

Document all AEs and SAEs from Study Day 1 through four weeks following the last dose of study drug.

All AEs and SAEs will be followed until resolution, even if this extends beyond the study-reporting period. Resolution of an AE is defined as the return to pretreatment status or stabilization of the condition with the expectation that it will remain chronic.

At any time after completion of the study, if the investigator becomes aware of an SAE that is suspected to be related to study product, the investigator will report the event.

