8.2 Secondary Efficacy Analyses

Logistic analyses will be utilized to determine if there is treatment effect based on the best ear outcome. As in the total ear analysis, change in the best ear will be categorized into binary outcomes – namely: improved + no change versus worse; improved + no change (normal to normal) versus worse + no change (abnormal to

abnormal); and improved versus other between baseline and Study Month 6. In addition to the primary outcome, we will analyze the binary outcome for change in the total ears categorized as: improved+ no change (normal to normal) versus worse and improved vs other.

For other secondary and tertiary outcomes, Fisher's exact test will be used to compare binary outcomes (such as detection of viruria or subject with at least one AE or SAE), and Wilcoxon Rank test will be used to compare continuous outcomes (such as quantitative log reduction) between the two treatment groups 6 weeks and 6 months after initial treatment.

Logistic model utilizing generalized estimating equations will also be used to determine the association between change in hearing and change in viral load. Change in viral load over time will be measured by the area under the curve computed using the trapezoidal rule. Spearman rank correlation will be utilized to examine the association between viral load and PK parameters. Poisson regression model will be used to compare the number of AEs/SAEs experienced by subjects between the two groups.

As in the primary outcomes, missing change in hearing outcomes will be replaced by worsened outcomes as sensitivity analyses for all secondary hearing outcomes.

The summary statistics will be produced in accordance with section 7.

9 Safety Analyses

Analyses of safety data will be based on data from all subjects receiving at least one dose of study drug. As per protocol, safety data will be collected only through Study Day 70, i.e., four weeks after the last study dose.

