9.2 Adverse Events

Analyses of AEs will be based on data from all subjects receiving at least one dose of study drug. As per protocol, safety data will be collected only through Study Day 70, i.e., four weeks after the last study dose.

AEs will be reported by treatment based on the relation to study drug, toxicity grade, and body system. When calculating the incidence of adverse events, or any sub-classification thereof by treatment, time period, severity, etc., each subject will only be counted once and any repetitions of adverse events will be ignored; the denominator will be the total number in each treatment group or overall sample size as appropriate.

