9.3 Deaths, Serious Adverse Events and other Significant Adverse Events

Analyses of SAEs will be based on data from all subjects receiving at least one dose of study drug. As per protocol, safety data will be collected from Study Day 1 through four weeks following the last dose of study drug.

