|---|-----|---------------------------------|---------------------------------------|----------------------|-----------------------------------|--|--|
| Table 6b: Summary Statistics of Baseline Age, Gestational Age and Birth Weight | 6b | Full Analysis | Age, Gestational Age and Birth Weight | Baseline | Therapy Group | N, N Missing, Mean, SE, Median, Min, Max | T-test or Wilcoxon |
| Table 7a: Summary of frequency count of CMV disease involvement | 7a | Full Analysis | CMV disease involvement | Baseline | Therapy Group | n, % | Fisher's exact |
| Table 7b: Summary CMV disease involvement: Lumbar Puncture | 7b | Full Analysis (where available) | CMV disease involvement | Baseline | Therapy Group | n, % | Fisher's exact |
| Table 7c: Summary of CMV disease involvement: Neuroimaging Results | 7c | Full Analysis (where available) | CMV disease involvement | Baseline | Therapy Group | n, % | Fisher's exact |
| Table 7d: Summary of Baseline Abnormal Findings | 7d | Full Analysis (where available) | Abnormality | Baseline | Therapy Group | n, % | Fisher's exact |
| Table 8a: Summary of Adverse Events | 8a | At least one dose of study drug | Adverse Events | Randomization-Day 70 | Therapy Group | n, % | NA |
| Table 9a: Listing of Each Subject's Serious Adverse Event | 9a | At least one dose of study drug | Serious Adverse Events | Randomization-Day 70 | Therapy Group | Listing | NA |
| Table 9b: Frequency of Serious Adverse Events by Body System, Grade and Therapy Group | 9b | At least one dose of study drug | Serious Adverse Events | Randomization-Day 70 | Therapy Group, Body System, Grade | n, % | NA |
| Table 10a: Frequency of Adverse Events by Therapy, Body System, and Grade* | 10a | At least one dose of study drug | Serious Adverse Events | Randomization-Day 70 | Therapy Group, Body System, Grade | n, % | NA |
| Table 10b: AE Grade by Therapy Group | 10b | At least one dose of study drug | Adverse Events | Randomization-Day 70 | Therapy Group, Grade | n, % | generalized linear mixed model for ordinal response with random intercept. |
| Table 10c: Listing of Adverse Events (Active Group) | 10c | At least one dose of study drug | Adverse Events | Randomization-Day 70 | NA | Listing | NA |
| Table 10c: Listing of Adverse Events (Placebo Group) | 10c | At least one dose of study drug | Adverse Events | Randomization-Day 70 | NA | Listing | NA |

| | | | | | | | |

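### AE and medical-visit windows tied to each child's last dose give early stoppers less observation time, and the SAP's Day 70 equals that window only when the last dose is on Day 42

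*Protocol*

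**What the plan says.** Three kinds of window are in play.

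- **Medically attended visits.** Protocol 3.2.2 and SAP 3.2 define the endpoint as "Incidence of unanticipated medically attended visits occurring from Study Day 1 through two weeks following the last dose of study drug".
- **AEs and SAEs, by last dose.** Protocol 9.2.2: "All AEs occurring from Study Day 1 through four weeks following the last dose of study drug must be documented appropriately regardless of relationship". Protocol 9.5.2: "Document all AEs and SAEs from Study Day 1 through four weeks following the last dose of study drug". Protocol 8.1.3 sets the same end for AE assessment at visits. SAP 9.3 agrees for SAEs: "safety data will be collected from Study Day 1 through four weeks following the last dose of study drug".
- **AEs, by calendar.** SAP 9.2: "As per protocol, safety data will be collected only through Study Day 70, i.e., four weeks after the last study dose". The opening of SAP Section 9 says the same. In the SAP Section 17 list, "Table 8a: Summary of Adverse Events" and the AE tables after it run from randomization to Day 70.

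Study visits are counted from Day 1, not from the last dose (Protocol Section 4). The Day 70 visit (7.4.4) lists an AE assessment without exempting early stoppers, but refers to Section 9 for it. Protocol 5.4.6 also sends the AEs of withdrawn or discontinued children to Section 9.

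Drug can be stopped for good before Day 42 (5.4.4 and 6.3). After an interruption for neutropenia, low platelets or raised ALT, treatment is not extended past six weeks.

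On analysis, SAP 9.2 takes the number of subjects as the AE denominator. SAP 8.2 and Section 9 compare AE counts by Poisson regression and mention no offset.

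A related point concerns safety labs. Protocol 8.2.1.1 says: "They will be collected at each study visit while the study subject is receiving valganciclovir and at the two week visit thereafter", and 8.2.1.2 says the same for chemistry. Section 7.4 has no visit two weeks after treatment; the next visit after Day 42 is Day 70.

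**The concern.** The SAP treats Day 70 and four weeks after the last dose as one date. For a child who stops early they are different dates, and the documents do not say which governs. Two sites could record such a child's later events differently and both claim to follow the plan.

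If the last-dose window governs, follow-up length depends on something that happens after randomization and that the drug can cause. Comparisons of AE counts, unrelated SAEs and medically attended visits would then rest on unequal observation time, which neither the denominator nor the stated model takes into account. Counts would tend to be lower in whichever arm has more early stops. The primary hearing endpoint is not involved.

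**Working it through.** **Inputs from the documents.** Scheduled last dose Day 42 (Protocol 7.4.3). Lags of 14 days (visits) and 28 days (AEs and SAEs). 27 children per arm (11.2). Permanent stops: 4 of 46 = 8.7% in the earlier intravenous ganciclovir trial and 1 of 24 = 4.2% in the earlier valganciclovir pharmacokinetic study (2.1.2.1).

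**Assumption.** The documents give no day of permanent stopping. I use Days 14, 28 and 35 as a range.

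**The plan's own figure.** Window end = last-dose day + lag. For a full course, 42 + 28 = 70, so the SAP's Day 70 is reproduced for a last dose on Day 42. The visit window for such a child ends at 42 + 14 = Day 56.

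**Early stoppers.**

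| Last dose | Visit window ends | Share of 56 days | AE window ends | Share of 70 days |
|---|---|---|---|---|
| Day 14 | Day 28 | 50% | Day 42 | 60% |
| Day 28 | Day 42 | 75% | Day 56 | 80% |
| Day 35 | Day 49 | 87.5% | Day 63 | 90% |

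None of the AE windows reaches Day 70.

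**Active arm as a whole.** Proportional loss = p × (42 − s) / W, with p the share stopped, s the stop day, and W = 56 (visits) or 70 (AEs).

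- p = 4/46, s = 14: 0.087 × 28 = 2.43 days per child; 2.43/56 = 4.3%, 2.43/70 = 3.5%.
- p = 4/46, s = 35: 0.087 × 7 = 0.61 days; 1.1% and 0.9%.
- p = 1/24, s = 14: 0.042 × 28 = 1.17 days; 2.1% and 1.7%.
- p = 1/24, s = 35: 0.042 × 7 = 0.29 days; 0.5% and 0.4%.

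Expected children affected: 27 × 1/24 = 1.1 to 27 × 4/46 = 2.3. If 20% stopped (assumed) at Day 14 to 28, the losses would be 5% to 10% for visits and 4% to 8% for AEs.

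**Effect on a proportion.** Assume a constant visit rate and a full-window incidence P. A child stopped at Day 14 then has incidence 1 − (1 − P)^(28/56). For P = 40% (assumed) that is 22.5%, and the arm average at 4/46 stopping is (42/46) × 40% + (4/46) × 22.5% = 38.5%. For P = 20% and 60% the arm averages are 19.2% and 58.0%.

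**Lab text.** Protocol 8.2.1.1 and 8.2.1.2 give totals of 2.5 mL and 5.0 mL over eight weeks. At 0.5 mL and 1.0 mL per draw (Appendix A notes), each is five draws, which matches Days 1, 14, 28, 42 and 70. Eight weeks ends at Day 56, however, and Day 70 is ten weeks.

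**The case against.** A window of last dose plus a lag is an ordinary exposure-based safety definition, and Day 70 may be no more than shorthand for the usual case. Visits stay on calendar days, Day 70 lists an AE assessment for everyone, and children off drug are encouraged to complete follow-up. On that reading AEs are collected to Day 70 in all children. This stands as far as it goes: for AEs the texts conflict, and under-observation is not demonstrated. No competing calendar text exists for medically attended visits.

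A reader might infer that toxicity stops come at about Day 14, because mean neutropenia onset in the earlier trial was 14.2 days. That figure is onset, not permanent stopping. Protocol 6.3.1 stops drug for good only after three confirmed falls. Onset plus one mean recovery is already 14.2 + 12.8 = 27 days, with two falls still to come, so neutropenia stops should tend to the late end of the range. In the other direction, a hold late in treatment may never resume, so permanent-stop rates may undercount early last doses.

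A reader might also infer that harms after an early stop are lost and the drug is made to look safer. The documents do not support that. A child stopped for toxicity already counts as having at least one AE, and each subject is counted once (SAP 9.2). AEs leading to permanent discontinuation are a separate endpoint. Known AEs are followed to resolution, and suspected related SAEs are reportable at any time (Protocol 9.5.2). Early stops can also occur on placebo: the rules are applied blinded, and 21% of untreated infants in the earlier trial had Grade 3 or 4 neutropenia.

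Finally, no item in Protocol 7.1 to 7.7, SAP schedule row or SAP table names the medical-visit endpoint. That does not show that sites are never asked about it: the case report forms and Manual of Procedures are not among the documents, and SAP 8.2 gives Fisher's exact test for other binary outcomes. It is missing detail.

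**Conclusion.** The inconsistency is real: the SAP's equation of Day 70 with four weeks after the last dose fails for any child whose last dose comes before Day 42. If the last-dose window governs, AE counts, unrelated SAEs and medically attended visits are observed for less time in such children, and the planned analysis does not allow for it.

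The likely size is small: about 0.5% to 4.3% less active-arm time for visits and 0.4% to 3.5% for AEs, with about 1 to 2 of 27 children affected. These figures assume that the earlier studies' stop rates carry over and that stops fall between Day 14 and Day 35. They describe the active arm alone; any early stops on placebo narrow the difference between arms. It is worth correcting because the correction is cheap and removes an ambiguity in what is recorded.

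**What to change.** 1. Preferably, set one calendar window for every dosed child, whenever drug stopped: medically attended visits from Day 1 to Day 56; AEs and SAEs from Day 1 to Day 70, or to four weeks after the last dose if that is later. Capture both at the existing Day 14, 28, 42 and 70 visits.
2. Alternatively, keep the last-dose windows and add log person-time as an offset in the Poisson models. For the medical-visit endpoint, count visits and model them in the same way.
3. Either way, correct the Day 70 statement in SAP 9 and 9.2, and align Protocol 3.2.2, 8.1.3, 9.2.2 and 9.5.2 with SAP 3.2, 9.3 and the time points in the Section 17 tables.
4. Name where medically attended visits are collected and add a row for them to the SAP table list.
5. Separately, reconcile the post-treatment lab visit in Protocol 8.2.1.1 and 8.2.1.2 with the Day 70 visit. No monitoring interval or lab rule is proposed here.

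The cost is wording in both documents, one table row and, if not already present, one case report form question. No visit is added. The small downside of the calendar window is that some late events unrelated to drug will be recorded.

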### **3.2.3. Tertiary Outcome Measures**

- Blood concentrations of ganciclovir after administration of valganciclovir

## **4. STUDY DESIGN**

This is a Phase II international, multi-center, double-blind, placebo-controlled evaluation of 6 weeks of valganciclovir treatment for children (up to 4 years of age) with virologically-confirmed congenital CMV infection and hearing loss. Patients who are between 1 month and 4 years of age and who have SNHL are eligible for enrollment on the study. **Enrollment on the study occurs when eligibility is confirmed and the informed consent is signed.** Following the signing of informed consent, the subject's Guthrie card will be retrieved and tested for CMV DNA by PCR unless there is a virologically confirmed diagnosis of congenital CMV infection made within the first 30 days of life. **Randomization on the study occurs when the diagnosis of congenital CMV infection is confirmed,** and the subject then is assigned to either receive 6 weeks of oral valganciclovir or 6 weeks of placebo. Study subjects will be stratified according to age at randomization (1 through 11 months, 12 through 23 months, 24 through 35 months, and  $\geq 36$  months) and CMV involvement (symptomatic and asymptomatic at birth) as a marker of disease severity. The sample size of randomized, evaluable subjects is 54. Dropouts and subjects with audiology assessments that are inadequate for study comparison will be replaced (up to 20%, or  $n=10$ ). Baseline study assessments (see Section 7.2) will be performed following randomization. Subjects will be followed for 6 months post randomization. During the six week treatment period, study subjects will be followed every 2 weeks. Subjects will also be seen at approximately one month following the final dose (Study Day 70), and again at Study Months 4 and 6.

At each of the visits during the treatment phase (Study Days 1, 14, 28, and 42), safety labs will be assessed; viral load specimens from blood, urine, and saliva will be obtained; adverse events will be assessed; and concurrent medications will be recorded. Ganciclovir concentrations for population pharmacokinetic assessment will be obtained at each study visit while the subject is receiving study medication. Dose adjustments for weight change will occur at study visits during the subject's treatment period, and may also occur at any time during the treatment period as indicated per protocol for neutropenia, thrombocytopenia, or renal impairment. At the Study Day 70 visit, safety labs will be obtained; viral load specimens from blood, urine, and saliva will be obtained; adverse events will be assessed; and concurrent medications will be recorded. Hearing will be assessed at baseline and at Study Month 6.

Changes in whole blood viral load measurements will be correlated with hearing outcomes. In study subjects with increasing whole blood viral loads during the course of treatment, antiviral resistance may be evaluated. A Data and Safety Monitoring Board (DSMB) will be established to oversee the accrual, performance, safety, and efficacy of the trial.

**Study Day 1** of the study is the day following randomization that the first dose of study medication is administered. "Study drug" refers to valganciclovir or placebo (for six weeks). Follow-up visits referred to by Study Day will be determined by calendar day from Day 1 (e.g., if Study Day 1 is June 20, then Study Day 7 will be June 26); follow-up visits referred to by Study

Month will be determined by calendar month (e.g., if Study Day 1 is June 20, then Study Month 1 will be July 20).

#### **4.1. Substudies (if applicable)**

None.

## 5. STUDY ENROLLMENT, RANDOMIZATION, AND WITHDRAWAL

### 5.1. Enrollment

Male and female infants from 1 month through 3 years of age (up to 4th birthday) with sensorineural hearing loss will be eligible for enrollment. **Enrollment on the study occurs when eligibility is confirmed and the informed consent is signed.** Following confirmation of inclusion/exclusion criteria and the signing of informed consent, the subject's Guthrie card will be retrieved and tested for CMV DNA by PCR unless there is a virologically confirmed diagnosis of congenital CMV infection made within the first 30 days of life. Enrollment will be implemented by the web-based enrollment system developed and maintained at the UAB Biostatistics Unit at the University of Alabama at Birmingham.

Clinicians who care for these patients (e.g., audiologists, otolaryngologists, pediatricians) will be made aware of the study so that they can inform the parents and guardians of patients with sensorineural hearing loss about the availability of the study.

### 5.2. Subject Inclusion Criteria

- Signed informed consent from parent(s) or legal guardian(s)
- Sensorineural hearing loss ( $\geq 21$ dB in one or both ears, documented within 12 weeks prior to study entry)
- Children from 1 month through 3 years of age (up to the 4th birthday)

### 5.3. Subject Exclusion Criteria

- Imminent demise
- Profound sensorineural hearing loss ( $> 90$ dB) in both ears
- Patients receiving other antiviral agents or immune globulin
- Gastrointestinal abnormality which might preclude absorption of an oral medication (e.g., a history of necrotizing enterocolitis)
- Documented renal insufficiency, as noted by a creatinine clearance  $< 10$  mL/min/1.73m^2 at time of study enrollment
- Breastfeeding from mother who is receiving ganciclovir, valganciclovir, foscarnet, cidofovir, or maribavir
- Infants known to be born to women who are HIV positive (but HIV testing is not required for study entry).
- Current receipt of other investigational drugs
- Previous receipt of ganciclovir or valganciclovir
- Known hypersensitivity to ganciclovir, valganciclovir, or components of the product

- Inability to attend follow-up hearing and clinical assessments
- Infants with Auditory neuropathy/dyssynchrony.
- Children with another known etiology for SNHL (e.g. connexin 26, syndrome or metabolic disorder associated with SNHL, inner ear malformation and widened vestibular aqueducts, meningitis). Exclusion of each of these conditions is not required for trial enrollment.

